2. SYNOPSIS

Study Title	A retrospective observational analysis of a cohort with Heart Failure with Preserved Ejection Fraction from a BNP pathway clinic
Problem statement	Heart failure with preserved ejection fraction (HFpEF) is a complex condition with various causes that is not yet fully understood. Most significantly there is no single method of diagnosing or treating the condition. Recently a novel non-invasive diagnostic criterion to predict the likelihood of HFpEF was proposed by Reddy et al. (2018) called H2FPEF. The main limitation of this study was the use of a single centre population from the Mayo clinic in Rochester, US. Another limitation is that the H2FPEF diagnostic criterion consists of common and often co-existing conditions which could as a result overestimate HFpEF probability. The aim of the investigators is to retrospectively test the H2FPEF criteria on the population at Queen Alexandra Hospital (QAH) in Portsmouth, which is of a lower socio-economic status and greater ethnic diversity. Implications of the project if H2FPEF is proved to be generalizable to the population is that it can be used within the Trust and rolled out to others. This would allow diagnosis to be made quicker and more cost effectively using echocardiography and without the need for invasive cardiac catheterisation. On the other hand if H2FPEF is found not to be applicable to the population then further research would be required to find the ideal diagnostic tool.
Research question / hypothesis	The investigator's hypothesis is that when H2FPEF criteria is compared against retrospectively held data for the patient population at QAH that this will overestimate the probability of HFpEF
Study Design	The study is a single-centre retrospective observational analysis
Study Participants	Patients who attended heart failure clinics at Queen Alexandra Hospital between January 1st 2016 – December 31st 2016
Planned Sample Size	2000
Follow-up duration	1 year
Planned Study Period	04/10/2019 – 30/04/2020
Primary Objective	The primary objective of the investigator's project is to test if the H2FPEF score accurately predicts HFpEF on the population at Queen Alexandra Hospital.

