Secondary Objectives	
 • Investigate if H2FPEF overestimates HFpEF diagnosis on the patient population when compared against known BNP levels. • To evaluate if H2FPEF can be validated on the patient population and be utilised to improve patient pathway for HFpEF. • To monitor patient responses to treatments and care for one year.
Primary Outcome Measure	To assess the predictive accuracy of H2FPEF at predicting HFpEF on the patient population as calculated by logistic regression, with diagnostic accuracy being assessed by sensitivity and specificity calculations.
Secondary Outcome Measures	
 • ANOVA will be performed to provide one simultaneous evaluation of the data to determine if there is a significant difference between

	H2FPEF score and diagnosis of HFpEF. •To assess number of hospital admissions and any changes in treatment/ care after one year for the population.
--	--

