In response Reddy et al (2018) recently proposed non-invasive diagnostic criteria called H2FPEF which assesses patients based on body mass index (BMI), the number of hypertensive medications they take, presence of AF, pulmonary pressure, age and filling pressure. The advantage of the H2FPEF score is that it uses only non-invasive echocardiography data alongside routine clinical data making it easy to derive. However one key limitation of their study is the population they used was all from the Mayo clinic and so the generalisability of their results has not been tested for other populations, such as those of lower socioeconomic status like in Portsmouth. A further limitation is the parameters chosen to create H2FPEF are all relatively common morbidities and usually co-exist, making it likely that it will over diagnose HFpEF.

Research questions:

The main research question the investigators are investigating is whether the H2FPEF criteria proposed by Reddy et al. (2018) is an accurate predictor of HFpEF on the patient population at QAH. In the original paper by Reddy et al. (2018) they created and tested H2FPEF criteria on their study population from the Mayo clinic, Rochester, US. This population is predominantly Caucasian and of a high socioeconomic status and so lacks generalisability. In response the investigators are testing the H2FPEF criteria on the population at QAH which is of a lower socioeconomic status, to investigate if it remains an accurate predictor of HFpEF.

Risks:

As the investigators study is a retrospective observational study there are no risks to participants, and all data obtained will be anonymised with no personally identifiable data being analysed.

Impact:

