8.2 Primary and Secondary Outcome Measures

Primary outcome measure

- Accuracy of H2FPEF at predicting HFpEF on the patient population will be assessed as specificity and sensitivity as calculated by logistic regression

Secondary outcome measure

- Investigate if H2FPEF overestimates HFpEF diagnosis on the patient population when compared against known BNP levels.
- To evaluate if H2FPEF can be validated on the patient population and be utilised to improve patient pathway for HFpEF.
- To assess patient outcomes after one year, including any changes in medication or treatment as well as number of hospital admissions and reported symptoms.

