13.2 Analysis of Outcome Measures

To determine if the H2FPEF score was accurate in predicting HFpEF the calculated H2FPEF score will be compared against BNP blood test results using the cut-off points stated by the European Society of Cardiology (Ponikowski et al., 2016). To test our hypothesis an analysis of variance test (ANOVA) will be performed to provide one simultaneous evaluation of the data to determine if there is a significant difference between H2FPEF score and diagnosis of HFpEF. A logistic regression analysis will then be carried out to give an odds ratio and provide a predictive analysis of the data. All statistical analysis will be performed using SPSS software.

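### The hypothesis is that H2FPEF overestimates HFpEF, but no statistic that measures overestimation is specified, and the ANOVA named as its test measures something else

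*Combined protocol and SAP*

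**What the plan says.** The synopsis (section 2) states the hypothesis: when the score is applied to the clinic's data, "this will overestimate the probability of HFpEF". Section 5 gives the reason. The score's components are common conditions that tend to occur together, "making it likely that it will over diagnose HFpEF". Under Impact, section 5 attaches consequences. If the hypothesis is accepted, the score needs optimising or replacing. If the null is accepted, the score counts as validated and could be used at this and other trusts.

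The measures named are these:

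- **Primary outcome, section 8.2:** accuracy "will be assessed as specificity and sensitivity as calculated by logistic regression". The synopsis speaks of predictive accuracy from logistic regression, "with diagnostic accuracy being assessed by sensitivity and specificity calculations".
- **Secondary outcome, section 8.2:** "Investigate if H2FPEF overestimates HFpEF diagnosis on the patient population when compared against known BNP levels". No statistic is attached to it.
- **Test of the hypothesis, section 13.2:** "To test our hypothesis an analysis of variance test (ANOVA) will be performed", looking for a difference between score and diagnosis.
- **Regression, section 13.2:** "A logistic regression analysis will then be carried out to give an odds ratio and provide a predictive analysis of the data".

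Section 8.1 gives the points for each component but no cut-off on the total. The documents name no predictive value, no calibration measure, no comparison of the number labelled with the number diseased, and no expected prevalence.

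**The concern.** Overestimation can mean two things here. One is over-diagnosis: the score labels more patients than the reference standard does, so false positives outnumber false negatives. The other is miscalibration: the probability attached to a given score is higher than the proportion of patients with that score who have HFpEF. The synopsis wording points to the second and section 5 to the first. Neither is estimated by the analyses that are named.

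The ANOVA matters most, because it is the declared test and section 5 ties adoption to the answer. Followed literally, the plan could reject a score that separates patients well, or call validated a score that does not separate them at all. In neither case would overestimation have been examined.

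**Working it through.** **Inputs.** From the documents: planned N = 2000 (synopsis); score range 0 to 9, from 2+1+3+1+1+1 (section 8.1); consecutive patients (section 8.1). The documents give no sensitivity (Se), specificity (Sp) or prevalence (p) for this clinic, so every such value below is an assumption and a range is shown. N = 2000 comes with no calculation, so there is no design figure to reproduce.

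**1. What the ANOVA tests.** With two diagnosis groups, its null is that the mean score is equal in patients with and without HFpEF. Set beside section 5:

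| ANOVA result | What it shows | Consequence if it decides the hypothesis |
|---|---|---|
| Significant (higher mean score in HFpEF) | The score separates patients | Hypothesis accepted; score to be optimised or replaced |
| Not significant | No separation shown | Null accepted; score validated |

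The consequence runs opposite to the finding in both rows.

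**2. What sensitivity and specificity leave open.** The score-positive fraction is q = Se·p + (1−Sp)(1−p). Net over-diagnosis means q > p, which holds when p < p* = (1−Sp)/[(1−Sp)+(1−Se)]. PPV = Se·p/q and NPV = Sp(1−p)/(1−q).

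With Se = Sp = 0.80, p* = 0.20/0.40 = 0.50. At N = 2000:

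| p | True cases | Score-positive | Ratio q/p | PPV | NPV |
|---|---|---|---|---|---|
| 0.10 | 200 | 520 | 2.60 | 0.308 | 0.973 |
| 0.50 | 1000 | 1000 | 1.00 | 0.80 | 0.80 |
| 0.80 | 1600 | 1360 | 0.85 | 0.941 | 0.50 |

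For p = 0.80: q = 0.64 + 0.04 = 0.68, and 0.68/0.80 = 0.85. The turning point moves with the pair: Se/Sp of 0.90/0.60 gives p* = 0.40/0.50 = 0.80, and 0.60/0.90 gives 0.10/0.50 = 0.20.

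**3. What the odds ratio leaves open.** In an illustrative simulation (400,000 patients, log-odds of −3 + 0.8 per point as the predicted model), the true intercept was shifted while the prediction, mean 0.534, stayed fixed.

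| Intercept shift | Observed proportion | Observed/expected | Odds ratio per point |
|---|---|---|---|
| 0 | 0.534 | 1.00 | 2.23 |
| −1 | 0.366 | 0.69 | 2.24 |
| +1 | 0.697 | 1.31 | 2.22 |

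The odds ratio is the same to within 0.02 whether the predictions are right, too high (shift −1) or too low (shift +1).

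**4. Whether predictive values alone would settle it.** With PPV = NPV = 0.80, q = 0.30 gives p = 0.80×0.30 + 0.20×0.70 = 0.38, ratio 0.79 (under-diagnosis). With q = 0.70, p = 0.62 and the ratio is 1.13 (over-diagnosis). A PPV/NPV pair without the positive fraction leaves the direction open too.

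**The case against.** The strongest reply is that overestimation is not ignored. It is a listed secondary outcome, the score is to be compared with BNP cut-offs, and the primary objective is accuracy, for which sensitivity and specificity are standard. That stands as far as it goes: it would be wrong to infer that no overestimation analysis is intended. What is missing is the statistic, and the one test assigned to the hypothesis does not supply it.

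Second, the cohort is consecutive, so prevalence by the reference standard will be a single known number and the ratio and predictive values can be worked out afterwards. This is correct. A reader might infer from the prevalence table that the study cannot answer its question; the documents do not support that, because the data will permit the answer. But a measure chosen after the data are seen is not pre-specified, and the plan already names a different test.

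Third, section 5's worry about common co-existing conditions could be read as a worry about false positives, which 1 − specificity measures directly. That is a fair reading of one sentence. It does not give net over-diagnosis, and it does not reach the synopsis hypothesis, which concerns probability.

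Fourth, the predictive analysis promised from the logistic regression might mean fitted probabilities, which do condition on the score. The text does not say so. A logistic model with an intercept, refitted in the same cohort, has a mean fitted probability equal to the observed proportion, so it cannot show that the original score's probabilities are too high.

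Fifth, the ANOVA sentence may have been meant as a comparison of two classifications of the same patients. If so, ANOVA is not the paired method for it, and a cut-off would still be needed.

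**Conclusion.** The point holds as a fault in the analysis plan, and it should be corrected before analysis. The central hypothesis has no statistic that measures it, and the named test can lead to the wrong conclusion under section 5's own reading of the result. The size depends on the clinic's prevalence and the score's accuracy, neither of which is given. At an assumed 80%/80%, the same pair is compatible with labelling 2.6 times as many patients as have HFpEF (10% prevalence) or 0.85 times as many (80% prevalence).

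Three stronger readings are not supported:

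- That the ambiguity exists at every cut-off. It requires sensitivity and specificity both below 100%. Calling every score of 0 or more positive gives Se = 1 and Sp = 0, which over-diagnoses at any prevalence below 1.
- That adding predictive values is enough. Step 4 of the working shows that it is not.
- That the design is at fault. Consecutive sampling makes prevalence observable.

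Any conclusion about overestimation is relative to the reference standard used. Section 13.2 names BNP; section 11.4 names ejection fraction and BNP.

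**What to change.** In sections 8.2 and 13.2:

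- **(a)** Pre-specify the cut-off on the 0–9 total that defines score-positive. Without it there is no two-by-two table.
- **(b)** Replace ANOVA as the test of the overestimation hypothesis with a paired comparison of score-positive and reference-positive patients: McNemar test and difference, and the ratio, each estimate with a 95% confidence interval.
- **(c)** Report PPV and NPV with 95% confidence intervals beside sensitivity and specificity, labelled as applying at this clinic's prevalence.
- **(d)** Tabulate the observed HFpEF proportion at each score with a 95% confidence interval, and compare it with predicted probabilities pre-specified from the original score publication. The documents do not give these, so they must be written into the plan.

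Base the conclusion on overestimation on (b) and (d). Reword section 5 (Impact) so that a non-significant result is not by itself read as validation.

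The cost is a few lines of plan text and one extra table. Section 11.4 already says that ejection fraction and BNP will be recorded, although the form in section 12.1 shows no column for either. The one statistical drawback is that predictive values hold only at this clinic's prevalence.

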9. STUDY PARTICIPANTS

9.1 Study Setting

Participants will have attended a heart failure clinic with a cardiology consultant at QAH between 01/01/2016-31/12/2016.

9.2 Overall Description of Study Participants

All participants will be patients who have attended heart failure clinics at QAH between 01/01/2016 – 31/12/2016. Eligibility will be met by the inclusion and exclusion criteria.

9.3 Eligibility Criteria

Inclusion Criteria

The participant must meet ALL of the following criteria to be considered eligible for the study:

- Age 18-85yrs inclusive
- Currently or previously attended a heart failure clinic with a cardiology consultant at QAH
- Had an echocardiogram, ECG, BNP blood biomarker test in addition to a routine clinical evaluation (including age, weight and number of hypertensive medications) during January 1st 2016 – December 31st 2016.

Exclusion Criteria

The participant may not enter the study if ANY of the following apply:

- Known structural heart disease
- Significant heart valve disease (greater than mild stenosis, greater than moderate regurgitation)
- Pulmonary arterial hypertension
- Constrictive pericarditis
- Pre-existing cardiomyopathy
- Heart transplantation

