8. STUDY DESIGN

8.1 Summary of Study Design

Data will be collected retrospectively from consecutive patients who meet the inclusion criteria to calculate a H2FPEF score: weight, number of hypertensive medications prescribed, presence of AF or not, presence of pulmonary hypertension or not, age and filling pressure. A total H2FPEF score will then be calculated for each patient as per Reddy et al. (2018) protocol: BMI > 30 kg/m² (2 points), ≥2 anti-hypertensive medications (1 point), paroxysmal or permanent AF (3 points), pulmonary artery systolic pressure >35mmHg (1 point), age >60 years (1 point), E/e' filling pressure > 9 (1 point).

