11.4 Study Assessments

All data will be collected retrospectively from the heart failure clinic database at QAH. Data will be collected on: weight, number of hypertensive medications prescribed, presence of AF or not, presence of pulmonary hypertension or not, age and filling pressure. These are the factors that make up Reddy et al. (2018) H2FPEF score. In addition the patient's ejection fraction and BNP will also be recorded as a measure to determine HFpEF diagnosis. All data will be anonymised and recorded on a Microsoft Excel spreadsheet, with a separate document documenting the pseudonymised data. All data will have been routinely collected as part of the heart failure patient pathway:

- Echocardiography - A non-invasive ultrasound test which takes approximately 30 minutes and has no radiation risk. Echocardiogram results will be used to ascertain pulmonary pressure and diastolic filling pressure. This will have been performed routinely as part of the heart failure patient pathway at QAH. All scans will have been performed on GE Healthcare Vivid echocardiography machines by a trained sonographer from the Cardiac Investigations Unit at QAH. A standard operating procedure exists for performing echocardiogram. In accordance with local practice personal protective equipment is worn for this test. ECG electrodes and ultrasound gel can be a potential risk to the patient with regards to dermatological reaction/sensitivity, however both are hypoallergenic substances.
- 12-lead electrocardiogram (ECG) - A non-invasive test of the electrical conduction of the heart assessing heart rate and rhythm. ECG results will be used to determine if the patient is in AF or not. All ECG will have been recorded with the use of the hospitals standard machine (MAC 1200, GE Healthcare). All tests will have been

performed by trained staff within the Cardiac Investigations Unit at QAH. Standard operating procedures are followed to perform ECG. ECG will have been performed routinely as part of the heart failure patient pathway at QAH.

- Weight - Using a standard trust scale (Marsden Weighing Company, UK)
- Age and Number of hypertensive medications taken - Assessed from patient records

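### Eligibility does not separate new referrals from patients whose heart failure was diagnosed or treated before their 2016 tests, and no planned variable would identify them

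*Combined protocol and SAP*

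**What the plan says.** **Who enters.** Section 9.1 states "Participants will have attended a heart failure clinic with a cardiology consultant at QAH between 01/01/2016-31/12/2016", and section 9.2 repeats the window: "All participants will be patients who have attended heart failure clinics at QAH between 01/01/2016 – 31/12/2016". The attendance criterion in section 9.3 carries no date: "Currently or previously attended a heart failure clinic with a cardiology consultant at QAH". A further criterion, "Had an echocardiogram, ECG, BNP blood biomarker test in addition to a routine clinical evaluation", is limited to calendar year 2016. All inclusion criteria must be met. The exclusions cover structural and valve disease, pulmonary arterial hypertension, constrictive pericarditis, transplantation and "Pre-existing cardiomyopathy". Earlier heart failure, HFpEF or heart failure treatment is not among them.

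**What the score is for.** The Synopsis says of a generalisable score: "This would allow diagnosis to be made quicker and more cost effectively using echocardiography". The Impact paragraph of section 5 likewise describes patients being diagnosed sooner and without catheterisation.

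**How the comparison is made.** Section 13.2 compares the score with BNP at guideline cut-offs; section 5 gives BNP above 35 pg/mL or NT-proBNP above 125 pg/mL. Section 11.4 adds ejection fraction. The score item in section 8.1 is "≥2 anti-hypertensive medications (1 point"), and section 11.4 gives its source: "Age and Number of hypertensive medications taken - Assessed from patient records". No rule covers indication or start date.

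**What is recorded.** The form in section 12.1 has the six score items, the total and patient outcomes. Section 13.3 limits collection to data for the score.

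**The concern.** A diagnostic score should be tested in the patients in whom it would be used, here people referred without a diagnosis. Under sections 9.1 to 9.3, a patient diagnosed before 2016 and seen and fully tested for review in 2016 is as eligible as a new referral.

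Two things could then go wrong even if every test is done on the same day. First, the reference takes no account of an earlier diagnosis: a known case whose BNP is at or below the cut-off under treatment counts as a non-case, and a high score in that patient counts as a false positive. Second, drugs started for heart failure might count towards the medication item and raise the score. Drugs taken for pre-existing hypertension are part of the score as designed and are not at issue.

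The study hypothesis is that the score overestimates HFpEF. Either mechanism would produce apparent false positives that favour that hypothesis. With no new-versus-review variable, the analysis could neither measure nor remove the effect.

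**Working it through.** **The plan's own figure.** The only design figure is the planned sample size of 2000. It cannot be reproduced, because no prevalence, expected accuracy, power or precision target is given. It serves below only as a total.

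**Step 1: does any criterion remove a review patient?** Attendance in 2016: met. All tests in 2016: met if they were repeated that year. Exclusions: none refers to earlier heart failure or its treatment. So a review patient tested in 2016 is eligible, and nothing in 12.1 or 13.3 marks that patient.

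**Step 2: effect through BNP.** Assumed inputs, none from the documents: 1000 true cases and 1000 non-cases, score sensitivity 80%, specificity 70%, 400 cases already treated, BNP otherwise a perfect reference. Let m be the number of treated cases that fall below the cut-off. Of these, 20% score negative and 80% score positive.

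Observed specificity = (700 + 0.2m) / (1000 + m)

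| Treated cases below cut-off | m | Observed specificity |
|---|---|---|
| 0% | 0 | 700/1000 = 70.0% |
| 10% | 40 | 708/1040 = 68.1% |
| 20% | 80 | 716/1080 = 66.3% |
| 40% | 160 | 732/1160 = 63.1% |

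Observed sensitivity is (800 − 0.8m)/(1000 − m) = 80% throughout. For scale, the 95% half-width for a specificity of 70% in 1000 non-cases is 1.96 × √(0.7 × 0.3/1000) = 2.8 points. The 10% row (1.9 points) lies inside that; the 20% row (3.7 points) and the 40% row (6.9 points) lie outside it.

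**Step 3: effect through the drug count.** The item is 1 of 2 + 1 + 3 + 1 + 1 + 1 = 9 points. Across the 32 yes/no patterns of the other five items, it changes the classification in 1 to 6 patterns, depending on the threshold (most at 5). The documents state no threshold, and the patterns are not equally common in practice.

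In the Step 2 model with m = 80, only 0.2 × 80 = 16 reclassified cases score negative. Even if the drug point moved all of them, specificity would fall only from 66.3% to 700/1080 = 64.8%.

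Suppose instead that half of cases and a quarter of non-cases are treated, and the drug point alone moves a share q of treated score-negatives over the threshold. Then:

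- specificity = 0.70 − 0.25 × 0.70 × q, which is 0.6825 at q = 0.1 and 0.665 at q = 0.2;
- sensitivity = 0.80 + 0.5 × 0.20 × q, which rises to 0.81 and 0.82.

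**Step 4: does a higher share of known cases offset this?** With sensitivity and specificity fixed, the ratio of score-positives to reference-positives is (0.8p + 0.3(1 − p))/p, where p is prevalence. It is 1.10 at p = 0.5, 0.93 at p = 0.7 and 0.83 at p = 0.9. A richer case mix therefore lowers this crude measure of overestimation. It does not change specificity, which with sensitivity is the primary outcome (section 8.2).

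**The case against.** A reader might infer from the section 9.3 wording that anyone who ever attended the clinic can enter. The documents do not support that: sections 9.1 and 9.2 require attendance in 2016, and 9.3 requires every test in 2016. The phrase may simply mean still attending or since discharged. Deleting it would leave the same patients eligible, so the gap is a missing restriction.

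A reader might also infer that treated patients do enter in number. That is not shown. The Synopsis title refers to a BNP pathway clinic, and sections 11.4 and 13.3 describe routine pathway tests at a clinic visit, which fits a diagnostic work-up. A review patient would need all tests again in 2016, and the structural disease and cardiomyopathy exclusions may remove some established patients. The share could be near zero.

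Finally, the direction of bias is conditional. No section says that treatment lowers BNP, still less below a cut-off as low as 35 pg/mL, or that heart failure drugs count as anti-hypertensives. Section 5 says that no effective HFpEF therapy has been found, although in the context of mortality and morbidity. If treatment moves neither item, this bias is absent.

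These points limit size and certainty, and they stand. They do not supply the missing restriction or the missing variable. The planned follow-up of medication changes (sections 8.2 and 10) suggests that some treatment data exist, but the 12.1 form has no baseline column for them.

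**Conclusion.** The point holds in a limited form. The documents themselves establish that eligibility does not exclude patients diagnosed or treated before their 2016 tests, that no planned variable identifies them, and that the intended use is new diagnosis. Applicability to undiagnosed referrals is therefore uncertain whichever way any bias runs.

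A fall in specificity towards the overestimation hypothesis follows only if treatment lowers BNP below the cut-off in some true cases or adds counted drugs. On the assumed inputs, the BNP route alone takes specificity from 70% (no effect) to 68.1% (10% of treated cases) or 63.1% (40%). The drug route adds little in that model. The stronger conclusion, that the design is biased towards the investigators' hypothesis, goes beyond the documents, because the share of review patients and both treatment effects are unknown. This is a cheap improvement, well short of a flaw that would invalidate the study.

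**What to change.** - **Section 9.3:** replace the undated attendance criterion with attendance between 01/01/2016 and 31/12/2016, consistent with 9.1 and 9.2. Define one index visit that supplies the score, the drug count and BNP.
- **Section 12.1:** add a new-versus-review column (heart failure diagnosis before the index visit, yes or no), taken from clinic attendance records during the eligibility screening that the direct care team already does under section 11.1. Amend section 13.3 so that this item may be collected.
- **Section 13.2:** make patients at their first attendance, without an earlier heart failure diagnosis, the primary accuracy population. Report all eligible 2016 attendees as a sensitivity analysis.

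The cost is one extra field and a smaller primary set, with wider intervals. The documents do not show that the database holds referral status or a date of diagnosis, so availability must be confirmed before the change is made.
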